6.2 Exclusion Criteria

Patients meeting any of the following criteria will not be permitted to enter the trial:

1. Any antineoplastic agent for the primary malignancy (standard or investigational) without delayed toxicity within 4 weeks or 5 plasma half-lives, whichever is shortest, prior to C1/D1 except:
 - Nitrosoureas and mitomycin C within 6 weeks prior to C1/D1
2. Part 2 ONLY:
 - a. Basket Cohort:
 - Prior therapy with *MET*-inhibiting agents

Note: Exceptions will be a subset of approximately 6 patients entered to the Basket Cohort after having received prior therapy with a MET-targeting TKI

- Prior therapy with antibody to HGF
- b. Basket Cohort and NSCLC MET-Amplified Cohort: Tumor status demonstrating *MET*-polysomy in the absence of *MET*-amplification, as specified

Note: Patients in the NSCLC *MET*^{Ex14Del} Cohort with polysomy are eligible.

- c. Radiotherapy against target lesions within 4 weeks prior to C1/D1, unless there is documented progression of the lesion following the radiotherapy

Note: Radiotherapy for pain control against non-target lesions is allowed, as long as it does not influence bone marrow function

3. Immunosuppressive or systemic hormonal therapy (> 10 mg daily prednisone equivalent) within 2 weeks prior to C1/D1 (for exceptions, see Section 7.5.2)
4. Use of hematopoietic growth factors within 2 weeks prior to C1/D1
5. Active second malignancy or history of another malignancy within the last 3 years, with the exception of:
 - a. Treated, non-melanoma skin cancers
 - b. Treated carcinoma *in situ* of the breast or cervix
 - c. Controlled, superficial carcinoma of the urinary bladder
 - d. T1a or b carcinoma of the prostate treated according to local standard of care, with prostate-specific antigen (PSA) within normal limits for the institution
6. Central nervous system (CNS) malignancy including:
 - a. Primary malignancies of the CNS
 - b. Known, untreated CNS or leptomeningeal metastases, or spinal cord compression; patients with any of these not controlled by prior surgery or radiotherapy, or symptoms suggesting CNS metastatic involvement for which treatment is required

Note: Patients with treated CNS metastases will be eligible if they are asymptomatic, do not require corticosteroids or anticonvulsants, and have confirmation of at least stable brain disease status as assessed by 2 imaging studies performed \geq 4 weeks apart with the most recent performed within 4 weeks prior to first trial drug administration

Patients with newly identified CNS metastases during study treatment will be considered to have PD and will be discontinued from treatment

7. Inadequate recovery from an acute toxicity associated with any prior antineoplastic therapy

Note: With the exception of persistent Grade 2 alopecia and/or peripheral neuropathy, patients must have recovered (to Grade \leq 1) from acute toxicity by C1/D1

8. Major surgical procedure within 4 weeks prior to C1/D1 or inadequate recovery from any prior surgical procedure
9. Non-healing wounds on any part of the body
10. Active thrombosis, or a history of deep vein thrombosis or pulmonary embolism, within 1 month prior to C1/D1, unless adequately treated and stable
11. Active uncontrolled bleeding or a known bleeding diathesis
12. Significant cardiovascular disease or condition, including:
 - a. Congestive heart failure currently requiring therapy
 - b. Class III or IV cardiovascular disease according to the New York Heart Association's (NYHA) functional criteria (30)
 - c. Need for antiarrhythmic medical therapy for a ventricular arrhythmia
 - d. Severe conduction disturbance (e.g., 3rd degree heart block)
 - e. Unstable angina pectoris (last episode at least 6 months prior to C1/D1)
 - f. Uncontrolled hypertension (per the Investigator's discretion)
 - g. Myocardial infarction within 6 months prior to C1/D1
13. Abnormal hematologic, renal or hepatic function as defined by the following criteria:
 - a. Absolute neutrophil count (ANC) $<1.5 \times 10^9/L$ (1500/mm³)
 - b. Hemoglobin ≤ 9 g/dL
 - c. Platelet count $<75 \times 10^9/L$ (75,000/mm³)
 - d. Serum creatinine $>1.5 \times$ upper limit of normal (ULN) for the institution
 - e. Aspartate aminotransferase (AST) $>3.5 \times$ ULN for the institution or AST $>5 \times$ ULN for the institution in case of known liver metastases
 - f. Alanine aminotransferase (ALT) $>3.5 \times$ ULN for the institution or ALT $>5 \times$ ULN for the institution in case of known liver metastases
 - g. Total bilirubin $>1.5 \times$ ULN for the institution
 - h. Prothrombin time as assessed by International Normalized Ratio (INR) $>1.5 \times$ ULN for the institution*
 - i. Partial thromboplastin time (PTT) $>1.5 \times$ ULN for the institution*
14. Any of the following within 2 weeks prior to C1/D1:

- a. Any serious or uncontrolled infection
- b. Any infection requiring parenteral antibiotics
- c. Unexplained fever >38.0 °C

15. Known or suspected hypersensitivity to any of the excipients of the Sym015 drug product

16. Any other life-threatening illness, significant organ system dysfunction, or clinically significant laboratory abnormality, which in the opinion of the Investigator, would either compromise the patient's safety or interfere with the evaluation of the safety of the trial drug

17. Any kind of disorder that compromises the ability of the patient to give written informed consent and/or to comply with trial procedures or is unwilling or unable to comply with trial requirements at the discretion of the Investigator

18. Breast feeding, or plans by the patient (or the patient's partner) to become pregnant during treatment or within 4 months after the end of treatment

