5.3.2 Screening

When the trial site identifies a patient suitable for screening, the Sponsor or designee should be contacted to ensure that a cohort is open for inclusion (applies to Part 1 only). With this assurance, the patient may be approached for informed consent. Screening activities may begin only once written informed consent has been obtained.

All patients giving informed consent to participate in the trial will receive a unique patient number. This number will identify the patient throughout the trial and will be composed of: a five-digit prefix, which identifies the country and site; a three-digit number, allocated sequentially starting from 001 for the first patient screened at the site, 002 for the second patient screened, etc.

The trial site staff must complete a Screening and Allocation Form, stating the allocated patient number along with the planned dates of screening and the day of first scheduled Sym015 administration (C1/D1). The planned date of C1/D1 will be agreed upon in collaboration with Sponsor or designee for the dose-escalation cohorts in order to ensure adequate time between dosing of the first patient and dosing of subsequent patients within each cohort (applies to Part 1 only). The completed Screening and Allocation Form will then be sent to the Sponsor or designee prior to or on the day of Screening.

Once eligibility has been confirmed in accordance with the inclusion and exclusion criteria, the Screening and Allocation Form will be fully completed and signed by the Investigator and resent to the Sponsor or designee. Sponsor or designee will approve each patient for start of treatment. A copy of the fully executed Screening and Allocation Form will be returned to the trial site for archiving. This form documents the allocated dose and dosing schedule of Sym015.

- Part 1: Patients in Part 1 with known *MET*-amplification who consent to optional biopsies will have a biopsy performed for biomarker analysis (archival tissue or tissue from a biopsy performed during screening as part of eligibility assessment may be submitted)
- Basket Cohort: All patients in the Part 2 Basket Cohort will have a tumor biopsy performed for biomarker analysis (tissue from a biopsy performed during screening as part of eligibility assessment is preferred, however archival tissue may be submitted at the Investigator's discretion).

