6. PATIENT SELECTION AND WITHDRAWAL

Questions regarding patient eligibility must be addressed and resolved by the Investigator in consultation with the Sponsor or designee prior to enrollment.

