17. CHANGES TO THE FINAL CLINICAL TRIAL PROTOCOL

Changes to the protocol will not be implemented without agreement from the Sponsor and prior review and written approval from the appropriate Health Authority (as indicated) and the IRB/EC, except where necessary to eliminate an immediate hazard to the patients. No protocol waivers will be allowed.

Protocol changes to eliminate an apparent hazard to trial patients may be implemented by the Investigator immediately. The Investigator must then, without delay, inform the local IRB/EC, and the Sponsor (or designee) will immediately notify local governing Health Authorities.

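### Exclusion 12e states its time window backwards: it bars remote unstable angina and does not name recent episodes

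*Protocol*

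**What the plan says.** Section 6.2 (Exclusion Criteria) opens with the rule that governs every item in it: "Patients meeting any of the following criteria will not be permitted to enter the trial". Criterion 12 begins "Significant cardiovascular disease or condition, including" and then gives sub-items a to g. Sub-item e is "Unstable angina pectoris (last episode at least 6 months prior to C1/D1". Sub-item g, two lines below, is "Myocardial infarction within 6 months prior to C1/D1".

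The synopsis carries the cardiovascular exclusion only as a general heading, with no angina item and no window. No other current text restates or corrects 12e, and the amendment tables in Section 21 record no change to it.

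Three provisions outside Section 6.2 bear on how the item would be applied:
- Section 6: "Questions regarding patient eligibility must be addressed and resolved by the Investigator in consultation with the Sponsor or designee prior to enrollment".
- Section 5.3.2: "Sponsor or designee will approve each patient for start of treatment".
- Section 17: "No protocol waivers will be allowed".

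**The concern.** In an exclusion list, meeting the item means exclusion. An item that is met when the last episode lies *at least* six months back excludes the lower-risk patient and leaves the higher-risk one unnamed. The parenthesis reads like a condition for acceptability that has been placed in a list of reasons for refusal.

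Two things are at stake:
1. **Recent unstable angina** is kept out only by the general stem of criterion 12, by criterion 16 and by case-by-case sponsor review. The item written to name it does not do so. Part 2 plans 15 to 27 sites, and an explicit rule is applied more uniformly than judgement.
2. **A remote episode** literally meets an exclusion. Because waivers are forbidden, a site that follows the text must refuse a patient who has no other therapeutic option. A site that enrols on the presumed intent records an eligibility deviation, and under Section 6.3.1 a significant one may lead to discontinuation.

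**Working it through.** No sample size, power or error rate enters this point, so the check is a reading of the text.

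**Step 1. Apply the item literally.** The two patients below are illustrations. The last column uses the window direction of item 12g.

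| Last unstable-angina episode before C1/D1 | 12e as written (*at least* 6 months) | 12e with *within* 6 months |
|---|---|---|
| 2 months | not met, so not excluded by 12e | met, excluded |
| 12 months | met, excluded | not met, so not excluded by 12e |

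The written rule gives the opposite result from the corrected rule in both cases.

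**Step 2. Compare with the other windows in Section 6.2.** These are all the windows counted back from C1/D1:

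| Criterion | Direction and length |
|---|---|
| 1, antineoplastic agents | within 4 weeks or 5 half-lives |
| 1, nitrosoureas and mitomycin C | within 6 weeks |
| 2c, radiotherapy to target lesions | within 4 weeks |
| 3, immunosuppressive or hormonal therapy | within 2 weeks |
| 4, growth factors | within 2 weeks |
| 8, major surgery | within 4 weeks |
| 10, thrombosis or embolism | within 1 month |
| **12e, unstable angina** | **at least 6 months** |
| 12g, myocardial infarction | within 6 months |
| 14, infection or fever | within 2 weeks |

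Total: 10 windows, 9 *within* and 1 *at least*. The nitrosourea line is grammatically an exception to criterion 1 and could be set aside. The count is then 9 windows, 8 *within* and 1 *at least*. Either way 12e stands alone. The closest comparator is 12g, which has the same criterion, interval and anchor but runs in the opposite direction.

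**Step 3. Ask whether the parenthesis could be a marked carve-out.** Where Section 6.2 relaxes an exclusion it says so: *unless* in 2c and 10, *with the exception of* in 5, *except* in 1, and a Note under 6 and 7. Item 12e has no such marker, so nothing in the text turns the parenthesis into a condition for entry.

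**Step 4. Ask what else catches a recent episode.** The stem of criterion 12 is non-exhaustive. Criterion 16 covers "Any other life-threatening illness, significant organ system dysfunction, or clinically significant laboratory abnormality, which in the opinion of the Investigator", would put the patient at risk or interfere with the safety evaluation. Sections 6 and 5.3.2 add sponsor consultation and approval. Together these would probably exclude recent unstable angina. None of them removes the literal exclusion of a remote episode.

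**The case against.** The strongest reply is that this is a clarification and not a safety gap. Most investigators would infer the intended meaning, namely that the last episode must lie at least six months back for entry. On that reading the threshold is sensible and agrees with 12g. The safeguards are also broad: medical history is taken at screening and again before first dosing, the investigator rechecks eligibility on C1/D1, and an ECG and an ECHO or MUGA are done at screening. Settling the meaning of an ambiguous criterion with the sponsor is arguably not a waiver, so Section 17 need not force a refusal.

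Much of this stands. The intended meaning can be guessed, and no enrolment of an unsafe patient is shown. The ECG and cardiac imaging do not date an angina episode, so they help only in part. Whether consultation with the sponsor may resolve the item against its plain words is open to argument.

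What does not stand is the claim that the text already says what was meant. Section 6.2 marks its carve-outs elsewhere, and 12e carries no mark. A rule that gives the right result only when it is not followed as written should be corrected.

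**Conclusion.** The point holds. Item 12e is wrong as written: its window runs in the opposite direction to the other nine C1/D1-anchored windows in Section 6.2, and nothing in the current protocol corrects it.

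The size is modest. The protocol gives no frequency of prior unstable angina, so the number of patients affected cannot be estimated and may be zero. Sample size, endpoints and the primary analysis are not affected. The item should nevertheless be fixed, because it is an operative safety criterion and the correction costs almost nothing. The conclusion assumes that the intent was to exclude recent episodes, as 12g does for infarction.

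**What to change.** Reword 12e as: Unstable angina pectoris (last episode within 6 months prior to C1/D1). This has the same form as 12g. The clinical team should confirm that six months is the interval they want.

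The cost is one phrase, carried in the next protocol amendment with the ethics approval and, as indicated, the Health Authority approval that Section 17 requires. Sample size, endpoints and analysis do not change.

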6.3 Withdrawal

The visit schedule for the treatment period will apply until Sym015 has been discontinued. Once this has occurred, an EOT Visit will be performed within 10 days following the decision to discontinue Sym015.

After EOT, the patient will continue to be followed for safety until 1 month (30 +7 days) after the last dose of Sym015, when the 1M FUP Visit must be completed.

6.3.1 Withdrawal from Treatment with Sym015

The patient must be withdrawn from treatment with Sym015 in the event of any of the following:

- A DLT considered by the Investigator to require treatment discontinuation. Refer to Section 9.5 for DLT definition (dose-escalation cohorts only)
- Occurrence of an AE considered by the Investigator to require treatment discontinuation
- Basket Cohort ONLY: Results from archival tumor tissue or a tumor biopsy submitted to confirm *MET*-amplification status that do not meet study eligibility criteria.

Note: Such patients may remain on study if there is evidence of an OR, SD, or other clinical benefit, but will not be included in the Evaluable for Response Population.

- PD, verified by CT/MRI according to RECIST v1.1
- Treatment failure not meeting the criteria for PD, but considered by the Investigator to require treatment discontinuation
- Requirement for a significant surgical procedure

Note: Patients requiring a minor surgical procedure (e.g., port placement, skin abscess drainage) may continue at the Investigator's discretion following discussion with the Sponsor or designee. A brief interruption in therapy may be considered

- An intercurrent illness which, in the opinion of the Investigator, would prevent completion of trial-related evaluations
- Use of prohibited concomitant medication, as defined in Section [7.5.2](#)
- Pregnancy
- Significant deviation from the eligibility criteria may require discontinuation after discussion with the Sponsor
- Noncompliance with trial procedures may require discontinuation after discussion with the Sponsor
- Patient withdrawal of consent and election to discontinue treatment. (Patients may leave the trial at any time for any reason if they wish to do so, without any consequences)
- Termination of the trial by the Sponsor
- Patients who meet Hy's Law criteria that cannot be explained by factors not related to Sym015.

Note: Patients meeting all three of the following are considered to have met Hy's Law criteria:

- The drug causes hepatocellular injury, generally shown by a higher incidence of 3-fold or greater elevations above ULN of ALT or AST
- Among trial subjects showing such aminotransferase elevations, often much greater than 3xULN, one or more show elevation of serum total bilirubin to ≥ 2 xULN, without initial findings of cholestasis (elevated serum alkaline phosphatase [ALP]).
- No other reason can be found to explain the combination of increased aminotransferase and serum total bilirubin, such as viral hepatitis A, B, or C; preexisting or acute liver disease; or another drug capable of causing the observed injury.

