7.1.4.3 Dose-Reduction for Sym015-Related Toxicities

Patients experiencing any of the following toxicities, assessed as possibly, probably, or related to Sym015, will have their dose reduced in accordance with the reduction schedule outlined in [Table 7](#).

1. Grade 3 non-hematologic toxicity regardless of duration, with the exceptions of:
 - a. Grade 3 nausea, vomiting, diarrhea, or fatigue lasting \leq 2 days with best supportive care
 - b. Grade 3 asymptomatic electrolyte abnormalities lasting \leq 3 days that are not considered clinically relevant by the Investigator and that resolve with medical therapy without requiring hospitalization
2. Any Grade 4 non-hematologic toxicity, with the exception of:
 - a. Grade 4 asymptomatic electrolyte abnormalities lasting \leq 3 days that are not considered clinically relevant by the Investigator and that resolve with medical therapy
3. Neutropenia that is:
 - a. Grade 3-4 febrile neutropenia
 - b. Grade 4 and sustained (i.e., ANC <500 per mm 3 , duration >5 days)
4. Thrombocytopenia that is:
 - a. Grade 3 with clinically significant hemorrhage
 - b. Grade 4 (platelets $<25,000$ per mm 3)
5. AST/ALT elevation $>3\times$ ULN with bilirubin elevation $>2\times$ ULN that cannot be explained by factors not related to study drug

Table 7 Sym015 Dose-Reduction Schedule

Allocated Dose	First Reduction	Second Reduction	Subsequent Reductions
6 mg/kg	3 mg/kg	1.5 mg/kg	Reduce by 50%
12 mg/kg	6 mg/kg	3 mg/kg	Reduce by 50%
18 mg/kg	12 mg/kg	6 mg/kg	Reduce by 50%
24 mg/kg	18 mg/kg	12 mg/kg	Reduce to 6 mg/kg, then by 50%

Note: In the event that an intermediate dose is explored in this study, dose-reductions in such cases will be to the next lower established tolerated dose level(s). If further dose-reductions are indicated, proceed as outlined above.

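### For a drug-related, unexplained rise in AST/ALT and bilirubin without initial ALP elevation, Section 6.3.1 requires withdrawal while Section 7.1.4.3 item 5 requires dose reduction, and neither section yields to the other

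*Protocol*

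**What the plan says.** Section 6.3.1 opens its list of events with a mandate: "The patient must be withdrawn from treatment with Sym015 in the event of any of the following". One entry concerns patients who meet Hy's "Law criteria that cannot be explained by factors not related to Sym015". A note then defines the criteria, beginning "Patients meeting all three of the following are considered to have met". Its three limbs are:

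- Aminotransferases: "The drug causes hepatocellular injury, generally shown by a higher incidence of 3-fold or greater elevations above ULN of ALT or AST".
- Bilirubin: "Among trial subjects showing such aminotransferase elevations", one or more reach total bilirubin of at least 2×ULN, "without initial findings of cholestasis (elevated serum alkaline phosphatase [ALP" being the abbreviation used).
- No alternative cause: "No other reason can be found to explain the combination of increased aminotransferase and serum total bilirubin".

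Section 7.1.4.3 is also mandatory. Patients with any listed toxicity "assessed as possibly, probably, or related to Sym015, will have their dose reduced in accordance with the reduction schedule outlined in" Table 7. Item 5 of that list is AST/ALT above 3×ULN with bilirubin above 2×ULN, not explained by factors unrelated to the drug. Items 1 and 2 carry written exceptions; item 5 has none. Section 6.3.1 does not mention 7.1.4.3, and 7.1.4.3 does not mention 6.3.1 or Hy's Law.

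**The concern.** The two sections prescribe incompatible actions for the same patient. An investigator managing a toxicity would naturally turn to 7.1.4.3, which addresses drug-related toxicities and gives a complete instruction: reduce and carry on. An investigator who turns to 6.3.1 would stop the drug for good. What is at stake is the safety of a patient with a possible drug-induced liver injury, and consistent handling across the 15 to 27 planned Part 2 sites.

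The wording of the 6.3.1 note adds to the difficulty. Its first two limbs describe how a drug behaves across a trial (a raised incidence, some subjects among others), not findings in one patient. The usable numerical trigger therefore sits in the dose-reduction section, and the safety-critical withdrawal rule is the harder one to apply.

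**Working it through.** No sample size, error rate or estimate is involved, so the check is a comparison of the two triggers and their consequences. Section 6.3.1 is read at patient level, because its bullet and the opening of its note both speak of patients who meet the criteria.

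| Element | 6.3.1 | 7.1.4.3 item 5 |
|---|---|---|
| ALT or AST | ≥3×ULN | >3×ULN |
| Total bilirubin | ≥2×ULN | >2×ULN |
| Initial ALP elevation | must be absent | not mentioned |
| Other cause | none found | none found |
| Causality to Sym015 | not explained by other factors | possibly, probably or related |
| Action | withdrawal, mandatory | dose reduction, mandatory |

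**Overlap.** A value above 3×ULN is also at least 3×ULN, and a value above 2×ULN is also at least 2×ULN. So every item 5 event meets the two laboratory thresholds of 6.3.1. If there is also no initial ALP elevation and no other cause, it meets 6.3.1 in full. The overlap is not empty.

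**Outside the overlap.** An event with initial ALP elevation falls only under item 5. An event with aminotransferases at exactly 3×ULN or bilirubin at exactly 2×ULN falls only under 6.3.1. Neither is in conflict.

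**Consequence.** Under 6.3.1 the next dose is 0 mg/kg. Under item 5 it is the first reduction in Table 7. Taking the 12 mg/kg maintenance dose as the allocated dose (an assumption, since Table 7 has no row for the 18-then-12 mg/kg regimen), that is 6 mg/kg every two weeks.

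**Does another section rank the two rules?**

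- 5.3.4 allows delay and/or reduction for toxicity and refers to 7.1.4. It gives no order.
- 7.1.3.2 (Part 1) keeps the allocated dose until withdrawal unless a reduction under 7.1.4 is needed. It gives no order.
- 7.1.4 says reductions may be required for specific toxicities. It gives no order.
- 7.1.4.2 holds dosing until the event recovers, with exceptions. Read with item 5, this means hold, wait, then re-dose at a lower level.
- Table 6, Grade 3 infusion reaction, states that either discontinuation or a reduced dose is open. Item 5 offers no such choice.

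**Evidence of intent.** The Summary of Changes is used here only to show purpose. Amendment 1 set out to stop therapy in all patients meeting Hy's Law. Amendment 4 later aligned dose-reduction criteria 2 and 5 with the DLT definition in 9.5.1, leaving 6.3.1 in place. This suggests the DLT item was carried into the reduction list without a carve-out for the existing withdrawal rule.

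**The case against.** The best defence is that the sections can be read together. A withdrawn patient has no dose to reduce, so 6.3.1 acts first and 7.1.4.3 governs only those who continue. The Protocol has a parallel: a Grade 4 infusion reaction falls under item 2 of 7.1.4.3, yet Table 6 requires discontinuation, also without a cross-reference. This reading is plausible and is almost certainly what the sponsor means, but it is written nowhere. Item 5 as it stands is a complete instruction to continue at a lower dose.

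A second objection is that the 6.3.1 note, taken literally, describes a trial population, so no single patient can meet it and no conflict arises. But the bullet and the note's opening both address patients, and a literal reading would leave the withdrawal rule without effect. That is a further reason to reword it.

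Third, there are safeguards. Section 6.3.1 requires withdrawal for any adverse event that the investigator judges to need it. Liver results must be reviewed before each dose (8.2.9). Section 7.1.4.2 delays re-dosing. The Medical Monitor, the Drug Safety physician and the SMC review safety (12.1, 12.2). These do reduce the risk. They do not correct the instruction: discretion to stop is different from a rule to stop, and the delay rule postpones the reduced dose without prohibiting it.

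Finally, the Amendment 5 entry in the Summary of Changes reports no DLTs in 12 Part 1 patients, and this liver event is a DLT under 9.5.1. That is reassuring, but it covers Cycle 1 in a small group and gives no usable rate.

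**Conclusion.** The contradiction stands in current text, confined to Sym015-related, otherwise unexplained AST/ALT above 3×ULN with bilirubin above 2×ULN and no initial ALP elevation. It rests on the patient-level reading of 6.3.1. It should be fixed because a mandatory rule, followed as written, would re-dose a patient after a suspected drug-induced liver injury. The number of patients exposed cannot be stated, since no event rate is given.

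Some stronger readings are tempting but unsupported:

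- *That the plan means to continue treatment after a Hy's Law event.* The mandatory wording of 6.3.1 and the purpose of Amendment 1 point the other way.
- *That every combined rise in aminotransferases and bilirubin is in conflict, so item 5 should be deleted.* Events with initial ALP elevation fall only under item 5 and still need its mandatory reduction.
- *That the reduction could be no reduction at all, by using the 18 mg/kg row of Table 7 (first step 12 mg/kg).* The 18 mg/kg is a single loading dose and all later doses are 12 mg/kg. A reading that leaves the dose unchanged defeats the instruction to reduce it. The missing row for this regimen is a separate matter.
- *That results are affected.* No efficacy estimate, sample size or safety table is made wrong.

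**What to change.** 1. In 7.1.4.3 item 5, add: *except events meeting the Hy's Law criteria in 6.3.1, for which Sym015 must be permanently discontinued*. Keep item 5 for events outside those criteria, such as those with initial ALP elevation.
2. Restate the 6.3.1 note as findings in one patient: ALT or AST ≥3×ULN, total bilirubin ≥2×ULN, no initial ALP elevation, and no other cause found.
3. State how the aminotransferase limb applies to patients who enter with AST/ALT already above 3×ULN. Exclusion criterion 13 admits values up to 3.5×ULN, or 5×ULN with known liver metastases, so a flat 3×ULN limit can be met at baseline. The bilirubin limb cannot, because entry requires total bilirubin no higher than 1.5×ULN. A rule relative to baseline for these patients would be enough; its exact form is a clinical decision.

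The cost is a wording amendment to two sections. No extra sampling is needed, since 8.2.9.2 already includes AST, ALT, ALP and bilirubin in the biochemistry panel assessed before dosing.
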